Yet, current policies and procedures requiring quarantine after close contact exposures to limit further spread have led to hundreds of thousands of missed school days and have threatened the school workforce, greatly impeding school operations and the ability of children to appropriately learn. In the fourth quarter of 2021 in NC alone, more than 40,000 students and staff were required to quarantine as a result of being a close contact of a COVID-19 case (unpublished). Fortunately, recent CDC and local guidance have eliminated quarantines for most exposed, unvaccinated, asymptomatic children who are wearing a mask and who are in close contact with another masked, infected child within the classroom setting. However, many quarantines continue to result in unvaccinated adults, children exposed to infected adults, and masked exposures occurring outside of the classroom (e.g., athletics or busing). Moreover, schools and local governments are steadily lifting mask mandates, even as local community cases rise, contributing to exponential increases in quarantines that not only keep children and staff out of schools and parents out of work, but have often overwhelmed school resources and the public health system.

To address the issue of quarantines while ensuring that the school and surrounding community remain safe from SARS-CoV-2 spread, some locales have begun implementing a "test to stay strategy", whereby a close contact undergoes serial testing over a specified duration of time.

The close contact must wear a mask during this time period but is not required to undergo quarantine as long as the screening tests remain negative and the contact remains asymptomatic. While this strategy is supported by strong scientific premise and initial data are promising, the impact of this strategy on quarantine, and secondary and tertiary within-school transmission has not been systematically evaluated.

This study will partner with schools to allow students and staff to remain in school following exposure if they continue to test negative for COVID-19 over pre-determined intervals. This study aims to collect data to assess the spread of SARS-CoV-2 in school communities with varying mitigation strategies to provide data-backed guidelines for mitigation strategies in schools. The study team will work with NCDHHS and a safety monitoring team on a weekly basis to interpret data, evaluate safety, and design next steps (e.g. testing frequency and timing).

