8.1.2 Secondary Endpoints

Secondary Objective #1: Characterize the effect of individual-level masking on SARS-CoV-2 spread.

Secondary #1 Endpoints:

- Proportion and number of masked students with positive COVID-19 test who were exposed to SARS-CoV-2 from masked versus unmasked individuals.
- Proportion and number of masked staff with positive COVID-19 test who were exposed to SARS-CoV-2 from masked compared to unmasked individuals
- Proportion and number of unmasked students with positive COVID-19 tests who were exposed to SARS-CoV-2 from masked compared to unmasked individuals
- Proportion and number of unmasked staff with positive COVID-19 tests who were exposed to SARS-CoV-2 from masked compared to unmasked individuals

Secondary Objective #2: Characterize the effect of exposure setting on SARS-CoV-2 spread.

Secondary #2 Endpoints:

- Proportion and number of students with positive COVID-19 test after indoor vs. outdoor exposure.
- Proportion and number of students with positive COVID-19 test after athletic vs. classroom exposure.
- Proportion and number of students with positive COVID-19 test after bus vs. classroom exposure.

Secondary Objective #3: Describe COVID-19-related school absences for up to 14 days following within-school SARS-CoV-2 exposure.

Secondary #3 Endpoints:

- Total number of school days missed due to symptoms after exposure.
- Total number of school days missed due to isolation after positive COVID-19 test.
- Total number of school days missed due to quarantine after SARS-CoV-2 exposure.

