8.2.1 Primary Analysis

For the primary endpoint the proportion of students/staff with positive COVID-19 test will be reported and the trend by week will be presented in graphical form. To account for the within-school correlation of outcomes, 95% confidence intervals will be estimated for the proportion using a generalized estimating equations approach using a working independence correlation structure.¹²

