8.2.2 Secondary Analysis

The proportion and number of students/staff who reported masking and unmasking will be reported and presented in graphical form. The primary analysis will be repeated for masked and unmasked participants (students and staff) separately. The primary analysis will be repeated for masked and unmasked source of exposure separately.

School absences will be analyzed by absences due to symptoms, positive COVID-19 test, or due to quarantine for exposure to SARS-CoV-2. To account for the within-school correlation of outcomes, analyses will be conducted using a generalized estimating equations approach using a loglink suitable for count outcomes, with a working independence correlation structure.

To account for within-school correlation, a risk between the schools using a generalized estimating equation approach with an identity link and a working independence correlation structure will be estimated. The risk difference will be estimated for each semester during the study period, as well as overall. Students will be censored by end of data or study withdrawal. Censoring will be addressed by incorporating inverse-probability censoring weights into the regression model, with censoring risk estimated with a Kaplan-Meier estimator.

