1.1 Specific Aims

- Evaluate severe acute respiratory syndrome coronavirus 2 (SARS-CoV-2) transmission following exposure in Kindergarten through 12th grade schools.
- Characterize the effect of individual-level mitigation measures (e.g., masking) on SARS-CoV-2 spread.
- Characterize the effect of exposure setting on SARS-CoV-2 spread.
- Describe COVID-19-related school absences for up to 14 days following within-school SARS-CoV-2 exposure.

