1.3 Endpoints

Primary Endpoints:

- Proportion of students with positive COVID-19 test following known within-school exposure.
- Proportion of staff with positive COVID-19 tests following known within-school exposure.
- Proportion of exposures undergoing the test-to-stay protocol that result in additional transmission.
- Time to test positivity among those exposed to SARS-CoV-2 and undergoing the test-to-stay protocol.

Secondary Endpoints:

- Secondary #1
 - Proportion of students with positive COVID-19 test following known within-school exposure.
 - Proportion of staff with positive COVID-19 tests following known within-school exposure.
 - Proportion of exposures undergoing the test-to-stay protocol that result in additional transmission.
 - Time to test positivity among those exposed to SARS-CoV-2 and undergoing the test-to-stay protocol.
- Secondary #2
 - Proportion of students with positive COVID-19 test after indoor vs. outdoor exposure.
 - Proportion of students with positive COVID-19 test after athletic vs. classroom exposure.
 - Proportion of students with positive COVID-19 test after bus vs. classroom exposure.
- Secondary #3
 - Total number of school days missed due to symptoms after exposure.
 - Total number of school days missed due to isolation after positive COVID-19 test.
 - Total number of school days missed due to quarantine after SARS-CoV-2 exposure.

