1.5 Primary Analysis

- Objective: The proportion of students/staff with positive COVID-19 test following known within-school exposure and the proportion of exposures undergoing the test-to-stay protocol that result in additional transmission will be summarized overall, by student or staff, by school district, by school level.
 - To account for the within-school correlation of outcomes, 95% CI will be estimated for the proportion using a generalized estimating equations approach using a working independence correlation structure (Zeger et al. 1988).
 - Objective: Days to test positivity among those exposed to SARS-CoV-2 and undergoing the test-to-stay protocol will be summarized by median and interquartile ranges and nonparametric estimate of test positivity probability will be plotted.

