2.8 Sensitivity Analysis

- Objective: Repeat the main analyses among study participants who had a positive test on or after the day of exposure
- Objective: Repeat the main analyses excluding athletic exposures and exposures acquired outside of school because of the higher risk of transmission previously documented in these settings.
- Objective: Broaden the main analyses for considered positives that include presumed positives, defined as those who developed symptoms but did not receive a subsequent negative test

Manuscript #3 Test-to-Stay in K-12 schools after Household Exposure to SARS-CoV-2

Date	June 14, 2022
Corresponding author	[name]; [name], BS
Lead statistician	[name]
Statistical advisor	[name]
Project leader	[name]
Target journal	TBD

History of changes

Date	Version	Summary of changes
May 6, 2022	1.0	Initial version
June 14, 2022	1.0	Clean up

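### SAP 1.3 repeats the primary endpoints under Secondary #1 in place of the protocol's four masking endpoints, and no planned analysis crosses contact mask with source mask

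*SAP*

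**What the plan says.** The protocol defines Secondary #1 in Section 2 and again in 8.1.2. It has four endpoints, one for each contact group: masked students, masked staff, unmasked students and unmasked staff. Each compares contacts by the mask status of the source. The first reads "Proportion and number of masked students with positive COVID-19 test who were exposed to SARS-CoV-2 from masked versus unmasked individuals".

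SAP 1.1 (Manuscript #1) keeps the matching aim: "Characterize the effect of individual-level mitigation measures (e.g., masking) on SARS-CoV-2 spread". SAP 1.3, however, fills Secondary #1 with the section's own four primary endpoints, beginning with "Proportion of students with positive COVID-19 test following known within-school exposure". Secondary #2 and #3 in the same section do follow the protocol.

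The analysis text is nearly the same in both documents. Protocol 8.2.2 and SAP 1.6 first repeat the primary analysis by the participant's own mask. A separate sentence then says "The primary analysis will be repeated for masked and unmasked source of exposure separately". Subgroup analysis (Protocol 8.2.3, SAP 1.7) is optional and unspecified. Manuscripts #2 and #3 plan no analysis by both masks.

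**The concern.** The SAP is the document the analyst will program from. Followed as written, it gives positivity by contact mask and positivity by source mask. It does not give the comparison the protocol names, which is masked against unmasked source within masked contacts and within unmasked contacts. A secondary objective of a study meant to inform school mitigation guidance would have no matching SAP endpoint and no matching analysis.

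There is a second gap. The protocol wording does not fix the denominator. It can mean the proportion positive among exposed contacts, by source mask, or the share of positive contacts who had a masked or an unmasked source. If the text is put back without settling this, two analysts could report figures that point in opposite directions.

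**Working it through.** The plan states no sample size, expected rate or effect for this endpoint, so there is no figure to reproduce. The check is a comparison of texts, followed by examples whose counts are all assumed.

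**1. Texts side by side.** All four bullets under Secondary #1 in SAP 1.3 are identical to the four primary endpoints above them, and none contains a masking term. All four protocol endpoints involve two masks, the contact's and the source's. SAP 1.5 summarises the primary proportions by student or staff, so the repeats in SAP 1.6 give role by contact mask and role by source mask. They do not give contact mask by source mask.

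**2. Can the one-way splits recover the cross?** Assume 500 contacts in each cell. Let the first letter be the contact and the second the source (m masked, u unmasked). Fix both one-way results at 30/1000 = 3% (masked) and 70/1000 = 7% (unmasked). With *mm* positives in the first cell, the margins force *mu* = 30 - *mm*, *um* = 30 - *mm* and *uu* = 40 + *mm*.

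| *mm* | Positivity mm, mu, um, uu | Unmasked minus masked source, masked contacts | Same, unmasked contacts |
|---|---|---|---|
| 5 | 1%, 5%, 5%, 9% | +4 points | +4 points |
| 10 | 2%, 4%, 4%, 10% | +2 | +6 |
| 15 | 3%, 3%, 3%, 11% | 0 | +8 |
| 25 | 5%, 1%, 1%, 13% | -4 | +12 |

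Every row has the same one-way results. The two differences sum to [(30 - 2*mm*) + (10 + 2*mm*)]/500 = 40/500 = 8 points, so with equal cells only their average (+4) is fixed. Even the sign among masked contacts is not.

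**3. Denominator.** Assume 900 masked contacts with a masked source at 2% and 100 with an unmasked source at 4%. Positives: 900 × 0.02 = 18 and 100 × 0.04 = 4. Among exposed contacts, positivity is twice as high after an unmasked source. Among positives, 18/22 = 82% had a masked source.

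**4. Exposure setting.** Protocol 1.1.1 says recent guidance has "eliminated quarantines for most exposed, unvaccinated, asymptomatic children who are wearing a mask" after classroom contact with another masked, infected child, while masked exposures outside the classroom still lead to quarantine. Enrolled masked/masked pairs may therefore differ in setting from other pairs. SAP 2.8 sets aside athletic and out-of-school exposures "because of the higher risk of transmission previously documented in these settings". Assume no source-mask effect at all, a risk of 6% in athletic and 2% in other settings, and athletic shares of 60% (masked source) and 20% (unmasked source) among masked contacts:

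- Masked source: 0.6 × 6% + 0.4 × 2% = 4.4%.
- Unmasked source: 0.2 × 6% + 0.8 × 2% = 2.8%.
- Crude difference: -1.6 points, against 0 within each setting.

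With shares of 40% and 20% the crude difference is -0.8; with equal shares it is 0.

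**5. Precision of a crossed contrast.** For 2% v 4%, the 95% half-width is 1.96 × sqrt[(0.02 × 0.98 + 0.04 × 0.96) × DE / n], where n is contacts per cell and DE an assumed design effect:

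| n per cell | DE = 1 | DE = 2 |
|---|---|---|
| 500 | 2.1 points | 3.0 points |
| 100 | 4.7 points | 6.7 points |

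Exact 95% intervals for a single proportion: 0/50 gives 0% to 7.1%; 2/100 gives 0.24% to 7.0%.

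**The case against.** Several points can be made for the plan.

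- **Masking has not been dropped.** SAP 1.1 keeps the aim and SAP 1.6 keeps two masking analyses. The repeated bullets could be read as the outcomes that 1.6 then breaks down by mask. The protocol itself does prespecify the crossed endpoints. All of this is fair, and it limits the defect to the SAP endpoint text and the analysis text of both documents. It does not supply the cross.
- **The denominator may be implied.** SAP General Statistics Principles uses participants with non-missing values, and the repeated primary analysis is positivity after exposure. This makes exposed contacts the more natural reading. But the general rule removes unknowns; it does not say whether the base is exposed contacts or positives, and the protocol's sentence structure allows either.
- **The numbers are assumed.** They are, and the fixed sum of 8 points holds because the cells are equal. With 900/100 masked and 500/500 unmasked contacts, moving one positive while holding the margins changes the first difference by 1/900 + 1/100 = 1.11 points and the second by 2/500 = 0.40, so the sum moves too. Unequal cells still leave the crossed results undetermined.
- **Contrasts by setting may be too imprecise to help.** The half-widths above bear this out at 100 per cell. That breakdown is a useful extra and not the core of the correction.
- **Timing.** The Manuscript #1 section is dated June 27, 2022, after Manuscript #2 had been submitted. Restoring endpoints the protocol already names is not a post hoc addition. A new risk difference is, and it should be labelled accordingly.

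**Conclusion.** The concern holds. SAP 1.3 does not carry the protocol's Secondary #1 endpoints, and neither document prespecifies an analysis that would produce them. That conclusion rests on the texts alone, reading the two sentences in SAP 1.6 and Protocol 8.2.2 as separate one-way splits, which is their natural sense.

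The documents give no counts, so the size can only be illustrated. With equal cells and fixed one-way results, the within-group differences shown run from +4 and +4 to -4 and +12 points, and the choice of denominator can reverse the apparent message. The repetition looks like a copying slip, but the documents do not say so, and the Manuscript #1 change history has no entry. The point should be corrected; it does not affect the primary endpoints.

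**What to change.** **SAP 1.3.** Replace the Secondary #1 bullets with the four protocol endpoints. State the denominator as exposed contacts in each contact-mask by source-mask cell.

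**SAP 1.6 and Protocol 8.2.2.** Report number and proportion positive in each cell, for students and staff separately. Use the interval already planned for the primary proportions in SAP 1.5 ("95% CI will be estimated for the proportion using a generalized estimating equations approach using a working independence correlation structure") and in Protocol 8.2.1, clustered by school.

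**Added contrast.** Within each contact-mask group, give the risk difference between unmasked and masked sources, with a school-clustered GEE interval where counts allow. Label it descriptive and record when it was added. Show it overall and, as a useful extra, by exposure setting.

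**Sparse cells.** Give an exact interval for the proportion only, marked as not adjusted for clustering, and no interval for the difference. Name the count that defines a sparse cell. SAP 3.7 already uses Clopper-Pearson for sparse data.

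**Unknown mask status.** Report the number of contacts affected, since the default denominator rule would drop them silently.

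**Cost.** Wording changes, a few tables and one descriptive contrast. No new data are needed: Protocol 5.3 (Enrollment/Baseline) already collects the contact's mask, the source's mask and the place of exposure. The drawback is imprecision in small cells, more so by setting.

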1 BACKGROUND INFORMATION AND RATIONALE

1.1 Background Information

1.1.1 COVID-19 and Kindergarten-12th grade school closures

Widespread Kindergarten through 12th grade school closures are the most important COVID-19-related threats to child health. Since February 2020, children have accounted for one-tenth of severe acute respiratory syndrome coronavirus 2 (SARS-CoV-2) cases; up to 2.2% and 0.04% of pediatric cases have resulted in hospitalization or death, respectively, and as many as 50% of cases are asymptomatic.^{1,2} However, children have been far from spared of the downstream effects of this pandemic. In March 2020, most Kindergarten through 12th grade schools preemptively closed to in-person education in an attempt to limit viral spread. Most publically-funded Kindergarten through 12th grade schools across the nation, responsible for educating >55 million of the nation's children, remained closed in the early 2020, citing concerns about viral transmission and risks to students and staff. Because public schools play such a vital role in the educational, social, and emotional development of young children as well as the delivery of vital services such as food and healthcare, it is not surprising that early data show food insecurity has doubled; 65% of children 9-13 years are less physically active; 1/6th of children have worsened behavioral health; suicidality may be increasing, and physical abuse is more severe.³⁻⁷ The potential consequences of these findings are deep and far-reaching; children with food insecurity are twice as likely to be in fair or poor health, more likely to be hospitalized, and more likely as adults to have poor job readiness. Chronic absenteeism in early primary school decreases the likelihood of reading at grade level by the third grade and increases the risk of drop out by 4 times compared to proficient readers.⁸ Adults with less than a high school education are 2.4 times as likely as high school graduates to rate their health as poor and live 10 years fewer than those with graduate education. Considering these profound impacts, access to in-person education is imperative.

In North Carolina (NC), schools have been able to show low secondary transmission of SARS-CoV-2 within school buildings.⁹ Data in school communities confirms that mitigation strategies such as proper masking have been imperative in reducing spread in schools.⁹⁻¹¹

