3.2 Study Definition of Enrollment

Study enrollment is defined as the participant has provided informed consent (or assent) and completed at least one day of testing in an effort to avoid quarantine.

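### Entry to avoid quarantine can tie exposure setting to masking among enrolled students, and the Secondary #2 athletic and bus versus classroom proportions have no masking stratification or adjustment

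*SAP*

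**What the plan says.** **Entry.** Protocol 3.2 defines an enrolled participant as someone who has consented and "completed at least one day of testing in an effort to avoid quarantine".

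**Who still faced quarantine.** Protocol 1.1.1 reports that recent guidance had "eliminated quarantines for most exposed, unvaccinated, asymptomatic children who are wearing a mask" and who were "in close contact with another masked, infected child within the classroom setting". It then lists what still led to quarantine: unvaccinated adults, children exposed to infected adults, and "masked exposures occurring outside of the classroom (e.g., athletics or busing").

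**The comparison.** Protocol 8.1.2 lists "Proportion and number of students with positive COVID-19 test after athletic vs. classroom exposure", with a matching bus endpoint. SAP 1.3 repeats both under Secondary #2, for example "Proportion of students with positive COVID-19 test after bus vs. classroom exposure". The aim they serve (SAP 1.1) is worded as an effect of exposure setting.

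**The analysis.** SAP 1.5 summarizes the primary proportions overall and by student or staff, district and school level; setting is not listed. SAP 1.6 and Protocol 8.2.2 repeat the primary analysis by participant mask and, separately, by source mask. The Secondary #1 endpoints in Protocol 8.1.2 cross the two mask variables with each other, but not with setting. The risk difference in Protocol 8.2.2 is between schools. No section gives an analysis for the setting endpoints.

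**The data.** Protocol 5.3 collects participant masking, source masking and place of exposure at enrollment.

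**The concern.** Whether a student has a reason to enter depends on setting and masking jointly. A masked student exposed to a masked classmate on the bus or in athletics still faced quarantine and had a reason to enroll. The same pair in the classroom mostly did not. Among enrolled students, masked-to-masked contacts may therefore be under-represented on the classroom side, even if masking was equally common everywhere to begin with.

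The protocol treats masking as related to the outcome: it says that "mitigation strategies such as proper masking have been imperative in reducing spread in schools". A factor that is linked to setting through entry, and to infection through biology, will distort a crude setting contrast.

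At stake is the reading of secondary objective 2. The study is meant to inform testing, quarantine and mitigation policy, and Manuscript #2 in the SAP (section 2.8) already has a sensitivity analysis that drops athletic and out-of-school exposures because earlier data showed more transmission there. A selection effect that could hide such an excess deserves a safeguard in the plan.

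**Working it through.** The documents give no attack rate, count or sample size behind this comparison, so there is no stated figure to reproduce. The mechanism is checked from the text and its possible size by a mixture calculation.

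**Step 1: the text, by type of student contact**

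| Contact | Classroom | Bus or athletics |
|---|---|---|
| Masked child exposed to masked child | Quarantine ended for most who were unvaccinated and asymptomatic | Quarantine continued |
| Masked child exposed to masked adult | Quarantine continued | Quarantine continued |
| At least one party unmasked | Outside the stated exemption | Outside the stated exemption |

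Only the first row differs by setting. It thins the classroom masked-to-masked cell and leaves the bus and athletic cells alone.

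**Step 2: inputs, all assumed**

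- pm: risk when both parties were masked, 2%
- pu: risk otherwise, 3% to 6%
- f: masked-to-masked share before the exemption, equal in both settings, 0.3 to 0.9
- e: share of classroom masked-to-masked contacts that do not enroll, 0.5 to 0.95
- True bus-to-classroom risk ratio: 1.00

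**Step 3: formulas**

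- Bus proportion = f·pm + (1 − f)·pu
- Classroom masked-to-masked share after entry, fc = f(1 − e) / [f(1 − e) + 1 − f]
- Classroom proportion = fc·pm + (1 − fc)·pu

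Example with f = 0.7, e = 0.8, pu = 4%:

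- Bus = 0.7 × 2% + 0.3 × 4% = 2.60%
- fc = 0.14 / 0.44 = 0.318
- Classroom = 0.318 × 2% + 0.682 × 4% = 3.36%
- Ratio = 2.60 / 3.36 = 0.77

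**Step 4: results with no true setting effect**

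| f | e | pu | Bus | fc | Classroom | Crude ratio |
|---|---|---|---|---|---|---|
| 0.3 | 0.5 | 3% | 2.70% | 0.176 | 2.82% | 0.96 |
| 0.5 | 0.8 | 4% | 3.00% | 0.167 | 3.67% | 0.82 |
| 0.7 | 0.8 | 4% | 2.60% | 0.318 | 3.36% | 0.77 |
| 0.7 | 0.95 | 6% | 3.20% | 0.104 | 5.58% | 0.57 |
| 0.9 | 0.95 | 6% | 2.40% | 0.310 | 4.76% | 0.50 |

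The first and last rows are the extremes of the range examined. If pu = pm, the ratio is 1.00 whatever f and e are.

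**Step 5: results with a true ratio of 1.5**

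The bus proportion is multiplied by 1.5. With pu = 4% or 6%, f = 0.5 or 0.7 and e = 0.8 or 0.95, the crude ratio lies between 0.86 and 1.23. At one end, 1.5 × 3.00% / 3.67% = 1.23; at the other, 1.5 × 3.20% / 5.58% = 0.86. A true excess can be diluted or reversed.

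**Step 6: what the direction depends on**

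The ratio is below 1.00 only while the non-classroom setting has a larger masked-to-masked share than enrolled classroom contacts. In the f = 0.7, e = 0.8 example that threshold is 31.8%. If masking in athletics were rarer than that, the crude athletic-to-classroom ratio would exceed 1.00 with no true effect.

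**Step 7: does stratifying work?**

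Within a mask cell the ratio is pm/pm or pu/pu times the true ratio, so the truth is recovered under this model. The classroom masked-to-masked cell may be thin: at e = 0.8 to 0.95 it holds 2% to 64% of classroom enrollees, against 30% to 90% of bus enrollees.

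**The case against.** The best defence has four parts.

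- **No one is excluded.** Protocol 4.1.2 and SAP 1.2 have no exclusion criteria, so exempt contacts could enroll. This stands. The mechanism is differential entry, and how uniformly participating schools applied the guidance is not documented.
- **The exemption is narrow.** It covers most, not all, of a group limited to unvaccinated, asymptomatic masked children with a masked child source. Masked classroom exposures to adults still enter. Protocol 1.1.1 also says mask mandates were being lifted; where few people mask, the masked-to-masked cell is small in every setting. This stands and limits the size. A reader might infer that the lower-risk cell is absent from the classroom side; the text supports only that it is thinned.
- **The SAP names endpoints and does not commit to a crude contrast.** True, but no setting analysis is specified, and unadjusted proportions are what the endpoint wording yields if followed as written.
- **The proportions are descriptive, secondary and untested.** As a description of positivity among test-to-stay participants they remain valid. The objective, however, speaks of an effect of setting, and that reading is not protected.

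Two stronger inferences also fail. A reader might conclude that bus and athletics will certainly look safer; this needs a similar masking mix across settings beforehand, which the documents do not give. A reader might also take all exposures with an unmasked party as a clean comparison because they led to quarantine everywhere. No section says so, and Protocol 1.1.1 states the exemption for unvaccinated children without addressing vaccinated contacts. That group also pools three mask combinations whose mix may differ by setting.

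**Conclusion.** The concern holds as a gap in the analysis plan. The documents themselves describe an entry route that depends jointly on setting and masking, they treat masking as protective, and neither protocol nor SAP stratifies or adjusts the athletic versus classroom and bus versus classroom proportions for masking.

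Direction and size are not established. If the masking mix was similar across settings before the exemption and masking lowers risk, the classroom looks relatively worse, and bus and athletics safer, than they are. Under the assumed inputs the crude ratio falls between about 0.50 and 0.96 when the truth is 1.00. The low end needs both a threefold risk difference by masking and 95% non-enrollment of classroom masked-to-masked contacts; the high end would be negligible. Less masking in athletics could cancel or reverse the effect.

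The argument concerns classroom versus non-classroom settings; it is not developed for the indoor versus outdoor endpoint. This is a worthwhile, inexpensive correction to a secondary objective and does not affect the primary endpoints.

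**What to change.** Amend SAP 1.3 and 1.6 as follows.

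1. Report student counts and positives by setting, participant mask and source mask.
2. Estimate the athletic versus classroom and bus versus classroom contrasts within the participant-by-source mask cells, or adjusted for both mask variables, using the school-clustered generalized estimating equations approach already planned.
3. Base each contrast on cells populated in both settings. Do not treat a pooled group with at least one unmasked party as like-for-like unless its mix of mask combinations is adjusted for.
4. Report the masked-to-masked classroom cell separately, with the caveat that it holds mainly contacts outside the quarantine exemption, for example those with adult sources. Adult or child source is not among the exposure details listed in Protocol 5.3, so this may not be separable in the data.
5. Label crude proportions by setting as descriptive of test-to-stay participants, not as an effect of setting.

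The cost is SAP wording and some table rows, since setting and both mask variables are already collected. The downside is wider intervals and some sparse cells, so some contrasts may have to stay descriptive.
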